By assessing immunity across different demographics (age and geographical area), this study aims to highlight specific populations at risk of measles outbreaks. This information will enable targeted public health interventions, such as tailored vaccination campaigns in areas or age groups with lower seroprevalence, ultimately improving overall vaccination coverage and preventing future outbreaks. Additionally, it will enable us to estimate the population's overall susceptibility to measles and monitor progress toward measles elimination goals (21).

In addition to assessing seroprevalence for measles, this study will also explore the seroprevalence of other biomarkers of infectious diseases that are of public health concern in Belgium. These may include diseases such as mumps, rubella, diphtheria, tetanus, pertussis and hepatitis, amongst others. A preliminary list of potentially included pathogens, along with the rationale for their inclusion, is provided in Appendix 1. This list is intended to support further discussions; final decisions on which pathogens will be included will be made in consultation with the steering committee. These data aid in identifying at-risk populations, guiding public health interventions, and providing a more accurate measure of disease burden, including underreported infections.

Proposed methods

Objectives

- 1. Establish a national serum bank to estimate the age-specific prevalence rates of biomarkers for infectious diseases in Belgium:
 - a. Estimate the measles seroprevalence in the Belgian population
 - across different age groups and geographical areas to identify potential gaps in immunity,
 - ii. identify risk factors for susceptibility (age, region),
 - iii. assess the relationship between immunity estimates and vaccination coverage,
 - iv. compare the findings with results from previous studies to interpret trends over time.
 - b. Estimate the seroprevalence of other pathogen-specific biomarkers in the Belgian population, based on the priority list determined by the steering committee, to guide public health interventions.

Study population

The target population of this study is the entire Belgian population. The study population consists of individuals living in Belgium, of all ages, who have had a blood sample analyzed at one of the laboratories participating to the sample collection during the sample collection time period.

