To prevent overrepresentation of immunosuppressed individuals, specific selection criteria will be implemented if the information about them is readily available. Samples should ideally be obtained from emergency, surgical/orthopedic, and otorhinolaryngology wards, as well as from first-line settings such as general practitioner (GP) consultations and private practices. Samples from oncology or intensive care units, as well as those with available information on immunosuppressed conditions or multiple transfusions, will be excluded. Samples should be obtained from individuals living in Belgium, with a registered Belgian postal code. These criteria have also been applied in previous Belgian sero-surveys (10,22,23).

Study design and period

This will be a cross-sectional study, providing a snapshot of the seroprevalence of biomarkers of pathogens under investigation at a single point in time, for the period from mid-2025 to mid-2026.

Operational definitions

- Seroprevalence: The proportion of individuals who have disease-specific biomarkers in their blood above a certain threshold as defined in literature, the specifications of the laboratory test, or, in absence thereof, in collaboration with the NRC of the related pathogen.
- Seroprevalence for measles: The proportion of individuals who have measles-specific IgG antibodies in their serum above the threshold of >120 IU/ml (considered to offer protection as defined in literature (24,25).

Sampling method

The sampling method used will be convenience sampling. We will collect leftover samples from participating laboratories of the Belgian sentinel laboratory network as they are easy to obtain and cost-effective to collect. Research has demonstrated that convenience samples of sera can yield immunity estimates for vaccine-preventable diseases that are comparable to those obtained from randomized cluster sampling methods (26,27).

Sampling procedure

Since 1983, Sciensano has managed a network of microbiological laboratories, called the Belgian sentinel laboratory network or *Epilabo*. This network relies on the voluntary participation of clinical laboratories spread throughout the country that send weekly data to Sciensano from routine clinical tests on a number of different pathogens (28).

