For each pathogen studied, we will calculate crude prevalence of seronegative, equivocal (if applicable) and seropositive results for Belgium. Since all collected samples will be tested for a certain pathogen by a single laboratory, we avoid any potential inter-laboratory variability in testing methodology. We assume that differences observed between laboratories reflect geographical variation rather than laboratory artifacts. However, since laboratories serve patients residing outside their province, the actual geographical distribution of samples may deviate from the intended stratification. To address this discrepancy, post-stratification weights will be applied to adjust for the spatial disparity between the data and the Belgian population. Moreover, seroprevalences will be adjusted for test sensitivity and specificity for the pathogen under investigation.

Statistical analysis will be done with R. Dummy tables are presented in Appendix 3. The specific analysis performed for each of the pathogens will be stored in an R file, containing explanation of the analysis. For each pathogen, these files will be stores in a secured folder at Sciensano.

Measles

For measles, measles vaccine target groups will additionally be defined as those targeted by measles vaccination (at least 1 year old and born in or after 1985) versus those not targeted (born before 1985, or not yet 1 year old at time of sampling). Within the measles vaccine-targeted group, two subgroups will be defined, with the 2-10 year olds as the ones targeted by minimal 1 dose and the 11-40 year olds as the ones targeted by 2 doses. The association between seronegativity and age group, sex, and province will be estimated using log binomial regression per measles vaccine target group. Adjusted prevalence ratios (aPR) and 95% confidence intervals (CI) will be calculated. P-values <0.05 will be considered significant.

The geometric mean titers (GMTs) for anti-measles IgG will be calculated and adjusted for clustered sampling and standardized for age, sex and population per province according to the Belgian population structure in 2025. The 95% confidence intervals (95%CI) will be estimated. Differences in GMTs between sex, region and age group will be assessed with the adjusted Wald chi-square test.

Quality assurance

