Second, serological testing has some intrinsic limitations. False positives or false negatives can occur due to the nature of serological tests. We will use validated assays to minimize error and perform confirmatory tests where necessary. Moreover, distinction between natural and vaccine-induced immunity (e.g. for measles) might not always be possible. Finally, interpretation of serological results and their clinical significance is not always clear. However, even if a cut-off or correlate of protection has not been established in the published literature, comparison of levels of biomarkers across different groups can yield valuable information.

Protection of human subjects

Vulnerable populations

The targeted population of this study is the entire Belgian population. The study population consists of individuals from Belgium, of all ages, who have had blood samples analyzed at one of the participating laboratories within the Belgian sentinel laboratory network. While vulnerable populations are included within the Belgian population and therefore might be included in the study population, vulnerable populations are not specifically targeted in this study.

Data collected are anonymous as only unique sample code, age, sex and arrondissement will be transferred. Hence, no identification will be possible.

Risks

As only leftover samples of blood/serum will be used, there will not be any direct risk/consequences on the health of the population under study.

The risk of sharing private or sensitive information about the study participants will be minimal. All data collected will be anonymous. All data will be stored at Sciensano on a secured and confidential file server. Access will be restricted to the study team, only through Sciensano-laptops.

Identifying information is not collected, therefore participating individuals cannot be informed about the results of the serological test (unlinked anonymous).

Benefits

This seroprevalence study, through its results and conclusion, will guide public health interventions and vaccination programs in Belgium. Hence, it will be beneficial for the Belgian community.

Confidentiality

See "Data collection – Data collection procedures".

Biological specimen

See "Samples collection and analysis".

Informed consent

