- [16] J. Schenk, S. Abrams, H. Theeten, P. Van Damme, P. Beutels, et N. Hens, « Immunogenicity and persistence of trivalent measles, mumps, and rubella vaccines: a systematic review and meta-analysis », *Lancet Infect. Dis.*, vol. 21, nº 2, p. 286-295, févr. 2021, doi: 10.1016/S1473-3099(20)30442-4.

5. Supplementary Materials of Appendix 5

[figure not shown]

Figure S1. Vaccination coverages (MMR1 in blue and MMR2 in orange) for (a) Flanders, (b) Wallonia, (c) Brussels.

[figure not shown]

Figure S2. Age structure of samples under the population-based allocation, based on 2021 demographic data.

[figure not shown]

Figure S3. Age distribution of samples under the survey-based allocation, based on the empirical age structure observed in the 2013 serological survey (measles).

sample size	structure	precision	overall prevalence
1000	sero	0,0195	0,903
1000	рор	0,0161	0,903
1000	unif	0,0184	0,903
2000	sero	0,0152	0,902
2000	рор	0,0123	0,903
2000	unif	0,0129	0,902
3000	sero	0,0120	0,903
3000	рор	0,0102	0,902
3000	unif	0,0110	0,903
4500	sero	0,0097	0,903
4500	рор	0,0089	0,902
4500	unif	0,0085	0,902

Table S1. Precision of the overall prevalence for measles.

[figure not shown]

Figure S4. Observed seroprevalence and smoothed estimates in 1993 for HBV. Age-specific seroprevalence (red dots with binomial confidence intervals) and fitted GAM estimates (black line) based on 1993 serological data. The generalised additive model was fitted using a complementary log-log link with a smooth term for age.

sample size	structure	precision	overall prevalence
1000	sero	0,01334	0,05541
1000	pop	0,01291	0,05489
1000	unif	0,01453	0,05473
3000	sero	0,00785	0,05511
3000	рор	0,00748	0,05491
3000	unif	0,00824	0,05443
6000	sero	0,00552	0,05482
6000	pop	0,00539	0,05488
6000	unif	0,00582	0,05473
9000	sero	0,00468	0,05471
9000	рор	0,00489	0,05498
9000	unif	0,00489	0,05501

Table S2. Precision of the overall prevalence for Hepatitis B.

[figure not shown]

Figure S5. Observed seroprevalence and smoothed estimates in 2011 for CMV.

Age-specific seroprevalence (red dots with binomial confidence intervals) and fitted GAM estimates (black line) based on 2011 serological data. The generalised additive model was fitted using a complementary log-log link with a smooth term for age.

sample size	structure	precision	overall prevalence
1000	sero	0,03476	0,349
1000	рор	0,03053	0,349
1000	unif	0,02886	0,348
3000	sero	0,02002	0,348
3000	рор	0,01585	0,348
3000	unif	0,01540	0,348

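### Prevalences are corrected for test sensitivity and specificity, but the log binomial model for seronegativity is specified without that correction, so its prevalence ratios can be biased

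*Protocol*

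**What the plan says.** Data analysis, General, sets out crude prevalences, post-stratification weights and then the correction for test error: "Moreover, seroprevalences will be adjusted for test sensitivity and specificity for the pathogen under investigation". Its stated object is seroprevalences.

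The measles subsection specifies the risk-factor analysis: "The association between seronegativity and age group, sex, and province will be estimated using log binomial regression per measles vaccine target group". The reporting follows: "Adjusted prevalence ratios (aPR) and 95% confidence intervals (CI) will be calculated", and "P-values <0.05 will be considered significant". Test error is not mentioned here. In the same subsection, the adjustments intended for the geometric mean titres (clustering; standardisation for age, sex and provincial population) are named.

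Bias and limitations accepts that serostatus is measured with error: "False positives or false negatives can occur due to the nature of serological tests". It relies on validated assays and, where needed, confirmatory tests, and does not mention an effect on the ratios.

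Appendix 3 tabulates percent seropositive (dummy table 2) and aPRs (dummy table 4) for the same variables: age, sex and region or province. Objective 1.a.ii, on risk factors for susceptibility by age and region, is the one that the ratios serve.

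**The concern.** The same serostatus variable is treated as error-prone in one analysis and, as specified, as error-free in the next. A standard log binomial fit to the observed result estimates ratios of apparent seronegativity, not of true seronegativity.

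The gap matters because the modelled outcome is the rare class. Some nine in ten people are expected to be seropositive, so even a 1% or 2% false-negative rate among them adds noticeably to a seronegative fraction of 5% or 10%. The effect is largest where true susceptibility is lowest.

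At stake is how differences between age groups and provinces are sized when catch-up vaccination is targeted. Dummy table 4 is planned for every pathogen, so the gap would recur as the serum bank is used.

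**Working it through.** **Inputs from the protocol.** Table S1 projects overall measles seropositivity of 0.902 to 0.903, so seronegativity is 9.7% to 9.8%. Table 5 gives age-specific half-widths. The protocol states no Se, Sp or prevalence ratio, so there is no stated figure on this point to reproduce.

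**Check of the baseline.** 1.96 × √(0.903 × 0.097 / 1000) = 1.83%; Table S1 gives 1.84% for the uniform design. At N = 4500, 1.96 × √(0.902 × 0.098 / 4500) = 0.87%, against 0.85%. A baseline of about 10% is sound.

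**Formula.** Let q be true seronegativity, with Se and Sp defined for IgG positivity. Apparent seronegativity is

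q* = q × Sp + (1 − q)(1 − Se) = (1 − Se) + q(Se + Sp − 1).

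With the same Se and Sp in both groups, the observed ratio is (c + q1)/(c + q0), where c = (1 − Se)/(Se + Sp − 1). For any informative test with Se < 1, c is positive and the ratio lies nearer 1 than q1/q0. If Se = 1, then c = 0 and the ratio is unchanged whatever Sp is.

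**Equal sensitivity; assumed true 10% v 5%, PR 2.00.**

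| Se | Sp | q* (10%) | q* (5%) | Observed PR |
|---|---|---|---|---|
| 1.00 | 0.95 | 0.0950 | 0.0475 | 2.00 |
| 0.99 | 0.99 | 0.1080 | 0.0590 | 1.83 |
| 0.98 | 0.98 | 0.1160 | 0.0680 | 1.71 |
| 0.95 | 0.95 | 0.1400 | 0.0950 | 1.47 |

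Inverting the formula in both groups returns 2.00 in every row.

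**A contrast nearer the protocol's own figures.** Reading Table 5 as a simple binomial (an assumption), q(1 − q) = n(h/1.96)². Ages 15-19 (n = 450, h = 1.95%) give q ≈ 4.7%. Ages 31-40 (n = 750, h = 2.40%) give q ≈ 12.9%. Both bands lie in the planned 11-40 subgroup. Taken as true values, the PR is 0.1291/0.0467 = 2.76. It would be observed as 0.1365/0.0558 = 2.45 at Se = Sp = 0.99 and 0.1439/0.0648 = 2.22 at 0.98.

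**How low can sensitivity plausibly be?** From the formula, q* cannot fall below 1 − Se. Ages 40-65 in Table 5 (n = 1050, h = 1.25%) imply q ≈ 4.5% on the same reading. Se = 0.95 would put a floor of 5% under apparent seronegativity, above that figure. So the 0.95 row is hard to reconcile with the protocol's projection; 0.98 and 0.99 are not.

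**Unequal sensitivity; Sp = 0.98.**

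- True 10% v 5%, Se 0.95 in the 10% group and 0.99 in the 5% group: 0.143/0.0585 = 2.44.
- True 10% v 10%, the same sensitivities: 0.143/0.107 = 1.34.
- True 10% v 5%, sensitivities reversed: 0.107/0.0965 = 1.11.

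**Power.** For 10% v 5% with 450 per group (illustrative; two-sided 5% normal-approximation test of two proportions), power is 81% with a perfect test, 76% at Se = Sp = 0.99 and 70% at 0.98.

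**The case against.** **The protocol is silent; it does not say that the ratios stay uncorrected.** The correction stands under General, the assay is still to be agreed with the reference centre, and a statistical analysis plan not shown may carry the correction into the model. This stands in part: it cannot be said that the ratios will be uncorrected, only that no correction is specified. But the protocol fixes the outcome, model, covariates, strata, effect measure and significance level. Followed as written, that model ignores an error the protocol corrects one paragraph earlier.

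**The threshold defines seropositivity.** The definition is "The proportion of individuals who have measles-specific IgG antibodies in their serum above the threshold of >120 IU/ml", so one could say the ratios concern that classification and nothing else. The same definition underlies the prevalences, which are corrected all the same.

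**A reader might infer that the two dummy tables contradict each other.** The documents do not support that. Table 2 is not labelled as corrected and shows marginal seropositivity; table 4 shows covariate-adjusted ratios, which the text estimates for seronegativity within vaccine target groups. The two need not match even with a perfect test. Test error adds a further numerical disagreement.

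**A reader might infer that every ratio shrinks towards 1, and by a lot.** That needs sensitivity below 1 and equal across groups. If sensitivity varies, for instance with antibody level, bias can go either way. Large effects also need sensitivity near 0.90 to 0.95, which sits badly with the low seronegativity implied for ages 40-65. That argument is itself limited: smoothing could make the binomial reading of Table 5 too low, the older cohorts are projected from observed 2013 results with no stated correction for test error, and the new assay may differ.

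**Immunity gaps do not rest on the ratios alone.** Objective 1.a.i is served by the corrected prevalences, and geometric mean titres are compared without a cut-off. This stands and limits the consequence.

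**Conclusion.** The point holds as a moderate flaw in the stated analysis: the correction is specified for prevalences and not for the seronegativity model that serves objective 1.a.ii. With sensitivity of 0.98 to 0.99, equal across groups, a true ratio of 2.0 (10% v 5%) would be reported as about 1.7 to 1.8. The bias is smaller at higher baseline seronegativity: for 19.6% v 9.8% the same values give 1.83 to 1.91. Sensitivity of 0.95 would give a larger bias but is hard to square with the protocol's projections. Specificity alone has no effect on the ratio, and unequal sensitivity leaves the direction open, so the uncorrected ratio cannot be taken as conservative.

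These sizes rest on assumed Se, Sp and group-specific seronegativity. A reader might also infer that correction would rescue contrasts that miss significance. It would not: it reduces bias in the estimate but does not restore power lost to misclassification.

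**What to change.** State that the aPRs use the same Se and Sp as the corrected prevalences. The preferred route is a misclassification likelihood:

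P(observed negative) = Sp × p + (1 − Se)(1 − p), with log p linear in the covariates.

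This keeps p above zero. Ratios of separately corrected prevalences can fail in small province strata. As an illustration, take 1050/11 ≈ 95 samples from ages 40-65 per province (assumed even), true seronegativity 3% and Sp 0.98. At Se 0.98, apparent seronegativity is 0.03 × 0.98 + 0.97 × 0.02 = 0.0488. The corrected value is zero or negative when at most 1 of 95 is observed negative (95 × 0.02 = 1.9), a binomial probability of about 5%. At Se 0.95 it is about 13% (at most 4 of 95, with q* = 0.0779).

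Report the standard log binomial aPRs alongside, labelled as describing apparent seronegativity, and show the corrected aPRs over a stated range of Se and Sp. Including values of Se that differ between groups would cover the case where the direction of bias is unknown.

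The cost is a protocol sentence or two, modest extra R code and somewhat wider confidence intervals. No new samples or data items are needed.

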For measles, the most recent national serological survey was conducted in 2013. To evaluate the sample size needed to estimate the current seroprevalence by age, we use a cohort-based modelling approach to project immunity levels to 2025. This model incorporates historical vaccination coverage, age of vaccination and waning immunity, following methods described by Hens et al. (2015) and Abrams et al. (2014) (30,31). The aim was to obtain both overall and agegroup-specific seroprevalence estimates with a precision of +-2% (width of confidence interval max. 4%). To ensure sufficient sample size of the serumbank for pathogens other than measles, these calculations were repeated for 2 additional pathogens. The additional pathogens (CMV and Hepatitis B) were selected based on their seroprevalence patterns in the population who differ importantly from the measles seroprevalence patterns.

Appendix 5 contains the full methodology and results. With a total sample size of 3,900 samples, precision of overall national seroprevalence estimates for all 3 pathogens would be <2% (and even <1% for measles and Hepatitis B). Not all agegroup-specific estimates would have <2% precision, but all are within acceptable ranges (all <3% precision for measles). To obtain equal precision in the region-specific estimates, similar absolute number of samples would need to be collected from Flanders, Walllonia and Brussels. However, as both the population size as well as

the number of labs in Brussels is much smaller than in Flanders, this is deemed unfeasible. We therefore plan a pragmatic approach and adjust the regional allocation to reflect practical constraints and the actual number of participating laboratories, accepting wider confidence intervals in Brussels. The final distribution of samples by agegroup is then presented in Table 1.

Table 1. Samples distribution - National

Age groups	Number of samples - National
1-4yo	450
5-9yo	450
10–14yo	300
15-19yo	450
19-31yo	450
31-40yo	750
40-65yo	1050
Total	3900

Sample collection and analysis

Sample collection and transport

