1.4. Simulation framework for sample allocation and precision

To assess the precision obtained under different age-based sampling structures, we simulated synthetic datasets by drawing binomial outcomes from the projected age-specific seroprevalence profile (Section 1.2). For each individual in the simulated sample, seropositivity status was assigned using a Bernoulli distribution with probability equal to the predicted seroprevalence at their age. This process was repeated independently 500 times for each sampling scenario. The resulting datasets were used to estimate the seroprevalence in each of the eight predefined age groups. Following the approach described by Blaizot et al. (2019) [1], precision was defined as half of the width of the 95% simulation-based confidence interval across the 500 replicates (simulation runs), calculated for each age group and overall. This framework enabled direct comparison of the expected estimation precision under each sampling design.

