To ensure sufficient precision for all pathogens, we selected the maximum number of samples per age group across the three pathogens as the final recommendation. This results in a total of 3,900 samples nationally, which we divide equally across the three regions, yielding 1,300 samples per region.

Table 4 reports the expected precision of the overall seroprevalence estimates under this allocation. At the national level (3,900 samples per pathogen), the expected precision is 0.82% for measles, 0.85% for hepatitis B, and 1.69% for CMV. At the regional level (1,300 samples per region), expected precision decreases slightly to 1.69% for measles, 1.45% for hepatitis B, and 2.64% for CMV, still within acceptable bounds.

Age group	Measles	НерВ	CMV
1-4yo	5%	5%	15%
5-9yo	15%	15%	5%
10-14yo	5%	10%	10%
15-19yo	15%	5%	10%
19-31yo	15%	10%	10%
31-40yo	20%	25%	15%
40-65yo	25%	30%	35%
Precision	0,88%	0,74%	1,52%

Table 2. Optimal proportion of samples per age group for measles, hepatitis B, and CMV based on national-level simulations.

	Measles	НерВ	CMV	National	Regional
1-4yo	150	150	450	450	150
5-9yo	450	450	150	450	150
10-14yo	150	300	300	300	100
15-19yo	450	150	300	450	150
19-31yo	450	300	300	450	150
31-40yo	600	750	450	750	250
40-65yo	750	900	1050	1050	350
Total	3000	3000	3000	3900	1300

Table 3. Absolute number of samples per age group, assuming 3,000 samples per pathogen. The final allocation (bold values) corresponds to the highest required count across pathogens, resulting in a total of 3,900 samples nationally (or approximately 1,300 per region).

	Measles	НерВ	CMV
National	0,82%	0,85%	1,69%
Regional	1,69%	1,45%	2,64%

Table 4. Expected precision (half-width of the 95% simulation-based confidence interval) for overall seroprevalence estimates under the final allocation. National precision is based on 3,900 samples; regional precision is based on 1,300 samples per region.

Precision by age - national allocation

_	.=			
Age group	Allocation	Measles	НерВ	CMV
1-4yo	450	2,25%	0,50%	4,23%
5-9yo	450	2,61%	0,53%	3,25%
10-14yo	300	1,76%	0,63%	3,50%
15-19yo	450	1,95%	0,73%	3,14%
19-31yo	450	2,88%	1,20%	2,94%
31-40yo	750	2,40%	1,51%	2,78%
40-65vo	1050	1,25%	1.42%	3.02%

Table 5. Expected precision (half-width of the 95% simulation-based confidence interval) for prevalence estimates of each age group under the final allocation.

4. References of Appendix 5

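### The stated measles precision (0.82% national, under 3% by age group) is sampling error for unadjusted seroprevalence, whereas the protocol commits to a sensitivity- and specificity-adjusted estimate, which is less precise

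*Protocol*

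**What the plan says.** **What will be reported.** Data analysis, General: "Moreover, seroprevalences will be adjusted for test sensitivity and specificity for the pathogen under investigation". The same section also plans crude prevalences. Bias and limitations accepts that assays misclassify some sera.

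**What precision is promised.** Sample size states that with 3,900 sera the "precision of overall national seroprevalence estimates for all 3 pathogens would be <2% (and even <1% for measles and Hepatitis B"; it adds that every measles age group is below 3%. Appendix 5, section 3 gives the exact figure: "At the national level (3,900 samples per pathogen), the expected precision is 0.82% for measles". Table 5 gives the age-group half-widths, the largest for measles being 2.88% at ages 19-31.

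**How that precision was obtained.** In Appendix 5, section 1.4, "seropositivity status was assigned using a Bernoulli distribution with probability equal to the predicted seroprevalence at their age", and "precision was defined as half of the width of the 95% simulation-based confidence interval across the 500 replicates (simulation runs". Section 1.5 uses the same kind of draw for the allocation search. No sensitivity or specificity appears in either section or in Tables 2 to 5 and S1.

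**What is not given.** No assay is named for measles, and there is no Se, no Sp and no validation sample size. Sample analysis leaves the method to agreement with the National Reference Center. The 0.96 in Appendix 5, section 1.2.2 is the seroconversion probability after vaccination, not an assay property.

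**The concern.** The precision is quoted for one estimator and the report will present another. Correcting for Se and Sp rescales the sampling error upwards and, where Se and Sp are themselves estimates, adds a second source of error. For measles this second source matters most, because prevalence is about 90%. Nearly all sera are then truly positive, so an error in Se moves the corrected prevalence almost one for one. It moves all ages and regions together, and collecting more sera does not reduce it.

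The results are meant to guide catch-up vaccination and to be read against elimination goals. A reader who takes the sub-1% figure as the precision of the reported national estimate would be more confident than the design allows.

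**Working it through.** **Inputs from the protocol.** N = 3,900; national measles half-width 0.82% (Table 4); age-group allocations and half-widths (Table 5); overall measles seroprevalence p of about 0.903 (Table S1, 0.902 to 0.903).

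**Assumed inputs.** Se, Sp and the number m of reference sera behind each of them. None is in the protocol, so a range is used.

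**Step 1: reproduce the stated figure.** Combine the Table 5 half-widths h_g with allocation weights n_g/3,900:

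sqrt(sum of (n_g h_g)^2)/3,900, with products n_g h_g = 1012.5, 1174.5, 528, 877.5, 1296, 1800 and 1312.5.

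The squares sum to 10,095,669, the root is 3,177.4, and dividing by 3,900 gives 0.815%, against 0.82% stated. Simple random sampling gives 1.96 x sqrt(0.903 x 0.097/3,900) = 0.93%. Sampling error alone accounts for the figure.

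**Step 2: half-width of the adjusted estimate.** The protocol gives no formula, so I use the standard correction (Rogan-Gladen): (apparent prevalence + Sp - 1)/J, with J = Se + Sp - 1. By the delta method the half-width has three parts, combined as a root sum of squares:

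- a = 0.82/J (sampling)
- b = 1.96 x sqrt(Se(1-Se)/m) x p/J (uncertainty of Se)
- c = 1.96 x sqrt(Sp(1-Sp)/m) x (1-p)/J (uncertainty of Sp)

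The weight p/J on Se is 0.92 at 99%/99%, 0.95 at 97%/98% and 0.97 at 95%/98%. National measles results, in percentage points:

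| Se/Sp | m per panel | a | b | c | Total |
|---|---|---|---|---|---|
| 99%/99% | 500 | 0.84 | 0.80 | 0.09 | 1.16 |
| 99%/99% | 1,000 | 0.84 | 0.57 | 0.06 | 1.01 |
| 97%/98% | 200 | 0.86 | 2.25 | 0.20 | 2.42 |
| 97%/98% | 500 | 0.86 | 1.42 | 0.13 | 1.67 |
| 97%/98% | 1,000 | 0.86 | 1.01 | 0.09 | 1.33 |
| 95%/98% | 500 | 0.88 | 1.86 | 0.13 | 2.06 |

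**Step 3: check the sampling term.** The table takes 0.82% as the half-width of the apparent prevalence, which favours the plan. If 0.903 is instead the true prevalence, the apparent prevalence at 97%/98% is 0.903 x 0.97 + 0.097 x 0.02 = 0.878. The sampling part then becomes 0.82 x sqrt(0.878 x 0.122/(0.903 x 0.097))/0.95 = 0.95, or 0.96 with unrounded values, and the total with 500 sera is 1.72%. The same step at 99%/99% with 500 sera gives 1.19%.

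**Step 4: when does the sub-1% figure survive?** At 99%/99% the total reaches 1% at about 1,300 sera per panel with the sampling term of Step 3, or about 1,100 with that of Step 2. With Se and Sp known exactly it stays below 1%: 0.87% at 99%/99% and 0.91% at 98%/98%, both with the Step 3 sampling term.

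**Step 5: the age-group statement.** For ages 19-31, 2.88/J exceeds 3% whenever J is below 2.88/3 = 0.96. At 97%/98%, 2.88/0.95 = 3.03% with Se and Sp known. At 99%/99% it is 2.88/0.98 = 2.94% with both known, and about 3.05% with 500 sera per panel (p = 0.903 is used here, since the age-group prevalence is not tabulated).

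**The case against.** **The plan does not fix Se and Sp as constants.** A reader might infer that it does, and that its intervals will be too narrow. The protocol does not support that. It has one sentence on the adjustment, gives no formula, and does not describe the interval for the adjusted estimate. The method may properly sit in an analysis plan that is not shown. What stands is the mismatch within this document between the precision it states and the estimator it commits to.

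**The figures do not strictly assume a perfect assay.** That reading is tempting, but for cohorts born up to 2000 the projected profile starts from 2013 test results with no correction mentioned (Appendix 5, sections 1.2.1 and 1.2.2). The simulated probability is then an apparent prevalence. Unadjusted seroprevalence is the accurate label.

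**The 0.82% is not an arithmetic error.** It reproduces, the measure is openly defined, and sampling precision is a usual planning quantity. This is correct; the figure simply does not belong to the adjusted estimate.

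**The design aim is ±2%, not 1%.** This is also correct. The 3,900 total comes from taking the largest allocation across three pathogens, and four of the six scenarios above still meet ±2% nationally. The calculation does not show that the sample is too small.

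**Every magnitude is assumed.** True for the sizes. That an imperfect assay widens the adjusted interval needs no assumed value.

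**Safeguards exist.** Crude estimates, validated assays, confirmatory tests and re-testing of 2013-2015 sera are planned. None of these supplies a value of Se or Sp, or its uncertainty.

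**Conclusion.** The point holds as a mismatch between stated precision and reported estimator. The sub-1% national figure and the under-3% age-group figures for measles are sampling error for unadjusted seroprevalence. The adjusted estimate that the protocol promises has a wider interval with any imperfect assay.

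The size depends on assumed Se, Sp and panel sizes and on the standard correction formula. Nationally it is about 1.2% at 99%/99% with 500 reference sera each, 1.7% at 97%/98% with 500, and 2.4% at 97%/98% with 200. At 99%/99% it stays at or under 1% only with about 1,300 or more sera per panel. The ±2% aim is met or missed depending on the assay and its validation. The statement that all age groups are below 3% fails at 97%/98% through ages 19-31, even with no uncertainty in Se or Sp.

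**What to change.** 1. **Sample size and Appendix 5, Tables 4 and 5:** label the precision figures as sampling error only, for unadjusted seroprevalence. The same simulation approach serves all three pathogens, so the label applies to every column.
2. **Once the assay is chosen:** restate the expected precision of the adjusted estimate, nationally and by age group, using that assay's Se, Sp and validation sample sizes. Step 2 above is enough; rerunning the simulation with misclassification is an alternative.
3. **Data analysis, General:** state that the uncertainty of Se and Sp is carried into the intervals of all adjusted seroprevalences, by a bootstrap or a Bayesian model using the validation counts, with estimates bounded at 0 and 100%. Show the adjusted results beside the crude ones already planned.

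Cost: analysis code, some wording, and a less favourable stated precision. No extra sera are needed.
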